## 6.2 Sample Size Determination

The table indicates the smallest detectable effects for a treatment X time interaction term given different sample sizes, assuming a Type I error rate of .05 and varying correlations between repeated measures, which ranged from .34 -.56 per outcome in the R03. Cohen defined f=0.10 and f=0.25 as small and medium effects, respectively. Thus our target N of 260 (N=200 + oversampling by 30% for attrition) will allow us to detect small-to-medium effects on continuous outcomes. Based on dichotomous clinical classification of opioid misuse data from the R03 (68% improvement for MORE versus 32% for SG), the proposed sample size will offer outstanding power (>.99) to detect differences of this magnitude on this outcome. (b) *Precision* of parameter estimation. Our target N will allow model parameters to be estimated with a high degree of precision. A per group sample size of N=130 provides 80% probability that a twosided 95% confidence interval will have a margin (half-width) less than +/- .18 standard deviation. Thus the proposed sample will provide precision more than adequate for estimating small clinical effects with high confidence. (c) *Multivariate models*. Generally, structural equation power calculations for the full information maximum likelihood sensitivity analyses can be based on Root Mean Square Error of Approximation (RMSEA) comparisons of nested models. The proposed sample provides, in a realistic testing scenario, greater than 80% power in a 1 df test (26 versus 25) of close fit comparing two models with RMSEA of .06 and .05 at  $\alpha$ =.05. These calculations are conservative. Maximum likelihood techniques retain all observations at all times, and efficiently incorporate correlated observations to yield an Effective Sample Size that is quantifiably larger than the number of subjects. With fully specified repeated dimensions, the anticipated correlations will yield an effective sample size that is 40% larger, or roughly N=360.

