# 8.2 Comparability of Treatment Groups

Comparability of treatment groups will be assessed by comparing the distribution of baseline characteristics in the two groups using appropriate graphical procedures, summary statistics and multivariate methods. The randomization is designed to produce balance on important covariates and baseline levels of the outcome measures. Nonetheless, some degree of prerandomization imbalance in study outcomes may occur, and we regress post-randomization observations on baseline scores to adjust for such imbalance.

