## 8.3 Analysis of the Primary Outcomes

Effects of treatment on opioid misuse and chronic pain symptoms will be evaluated using linear and nonlinear mixed models with fixed effects consisting of a time factor and between-subjects treatment factor (MORE vs. SG), and will adjust for randomization imbalance by covarying baseline levels of the outcome. For the continuous pain symptom outcome measured by the

Brief Pain Inventory (BPI), the longitudinal trajectory for individual i on outcome j in treatment group g at post-randomization time t is modeled, under the full-rank parameterization, as

$$(1) \ \ y_{ijg,t>1} = a_{ijg} + \beta y_{ijg,t=1} + \mu_{jg,t>1} + \varepsilon_{ijg,t>1} \ \ , \ \ a_{ijg} \sim N(0,\psi_j) \ , \varepsilon_{ijg,t>1} \sim MVN(0,\Theta_j) \ ,$$

 $a_{ijg}$  is a random intercept with zero mean and variance  $\psi_i$ ,

 $\beta$  is the fixed regression coefficient of the post measures on pre-randomization baseline (time 1) score  $y_{ii\alpha,t}$ =1

 $\mu_{jg,t>1}$  are the post-randomization treatment arm means at times 2 through 5, conditioned on baseline, equivalent in this parameterization to distinct intercept terms

 $\mu_{jgt>1} = E(y_{ijg,t>1} \mid a_i, y_{ijg,t=1})$  for each group and time, and  $\epsilon_{ijg,t>1}$  are multivariate normal random error terms assumed to follow either an independent scaled diagonal or AR1 error structure, as determined by comparison of BIC model statistics.

Opioid misuse as measured by the Drug Misuse Index (DMI) is a dichotomous longitudinal variable Y, and we will evaluate treatment impact with a generalized linear mixed model specifying a binary distribution and logit link, with time t and group g as categorical factors and a random intercept  $\zeta_i$ :

$$\log(\pi_i / (1 - \pi_i)) = \alpha_g + \beta_t + \gamma_{gt} + \zeta_i$$

$$Y_{igt} \mid \zeta_i \sim Bernoulli(\pi_{igt}), \ \zeta_i \sim iid \ N(0, \psi)$$

For the opioid misuse outcome (Drug Misuse Index; DMI), it is not necessary to adjust for baseline differences, as all participants exhibited opioid misuse at baseline.

Our primary interest lies in estimating, for the BPI co-primary pain outcome j, the adjusted main effect, which represents the overall benefit of treatment across all four post-treatment measurement points conditional on baseline:

(2) 
$$\hat{\delta}_j = (1/4) \sum_{t=2}^{t=5} \hat{\mu}_{g=SG,t} - \hat{\mu}_{g=MORE,t}$$

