# 8.4 Analysis of the Secondary and Tertiary Outcomes.

Analysis of opioid medication dose will also be implemented as a linear mixed effects model of longitudinal morphine equivalent intake, conditional on baseline, under a log transformation to reduce skew. Distress and other psychological outcomes will similarly be analyzed using linear mixed models adjusted for randomization imbalance by covarying baseline levels of the outcome. Exact unadjusted p-values are reported for the secondary and tertiary outcomes. As in the analysis of our continuous primary outcomes, our primary interest lies in the adjusted main effect of treatment, which with this model specification represents the average effect of treatment across all post-treatment measurement points.

Control for multiple comparisons among the secondary and tertiary variables is provided by a global hypothesis test evaluated at alpha=.05 in the multivariate mixed effects model as  $H_{0,\mathrm{joint}}: \forall j, \delta_j = 0$  versus  $H_{1,\mathrm{joint}}: some \ \delta_j \neq 0$  for some j. Multivariate contrasts may be

implemented in the univariate mixed model framework of SAS 9.4 by introducing a categorical indicator variable for outcome j, interacting this variable with all other effects, and specifying distinct covariance matrices for each j. The global net benefit hypothesis is a custom contrast with J df, where J is the number of non-primary outcomes. Rejection of the global hypothesis test implies a significant treatment impact on at least one secondary outcome j, and we report exact p-values for the univariate tests.

Descriptive analysis of opioid dosing data will examine group differences in the proportion of participants who achieve an opioid dose reduction of ≥50% at each time point.

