To explore whether the cognitive, affective, and physiological mediators specified in Aims 2 and 3 statistically mediate the effect of treatment on outcome variables, we will conduct structural equation path analyses according to established guidelines by evaluating three regression paths: A) 'a' path between treatment indicator and change in outcome (e.g., opioid misuse) from pre-treatment to follow-up; B) the 'b' path between pre-post treatment change in the mediator (e.g., attentional bias) and pre-treatment to follow-up change in the outcome (e.g., opioid misuse); and C) the 'c' path between treatment and pre-post treatment change in the mediator (e.g., attentional bias). We will test mediation by evaluating the significance of the joint product of the a and b paths, with bootstrapping used to test the significance of the indirect effect. Our team developed a comprehensive analysis of mediation under possible moderation for clinical trials, allowing for the possibility that treatment has changed relationships, not just levels, among variables - this will further guide analyses for Aims 2 and 3. Path models will be corrected for multiple comparisons. Mediational analyses will be published in a subsequent report following publication of the primary trial outcomes.

For EMA, we will use growth curve analysis to examine treatment and homework practice effects on: trajectories of craving (and other tertiary EMA outcomes – e.g., affective state). The basic growth curve model will be specified with fixed effects consisting of continuous time t (in days), categorical period p (AM, Noon, or PM reporting) and the categorical between-subjects treatment factor (g = MORE vs. SG). Random effects will incorporate correlated intercept and period-specific trend components, as in standard growth models:

$$y_{itpg} = b_{0i} + b_{1ipg}t + \varepsilon_{itpg} ; b_{0i}, b_{1ipg} \sim MVN([\beta_{0p}, \beta_{1pg}]', \Psi), \varepsilon_{itpg} \sim N(0, \sigma^2).$$

The model allows different trends in the three different reporting periods of the day. The key null hypothesis of treatment impact in EMA will be evaluated by testing the equality of the three fixed effect period trends between arms:

$$H_0: \sum_{p} \beta_{1p,g=SG} / 3 = \sum_{p} \beta_{1p,g=MORE} / 3 = \sum_{p} \beta_{1p} / 3$$

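### The mediation models put the treatment-to-mediator path, and the treatment-to-outcome path for continuous outcomes, on change scores with no baseline covariate, which loses precision that the plan keeps elsewhere

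*SAP*

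**What the plan says.** The mediation paragraph of SAP section 8.4 defines three paths:

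- Treatment to outcome (labelled a), with the outcome taken as change from pre-treatment to follow-up.
- Mediator to outcome (labelled b), relating "pre-post treatment change in the mediator (e.g., attentional bias) and pre-treatment to follow-up change in the outcome (e.g., opioid misuse").
- Treatment to mediator (labelled c), the "path between treatment and pre-post treatment change in the mediator (e.g., attentional bias").

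No baseline covariate is named for any of them. The paragraph cites guidelines and the team's own mediation method, calls the work exploratory, and leaves it to a later report.

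For the treatment comparisons the SAP is explicit about baseline. Section 8.2: "we regress post-randomization observations on baseline scores to adjust for such imbalance". Model (1) in section 8.3 gives the BPI a freely estimated baseline coefficient. Section 8.4, a few paragraphs before the mediation text: "Distress and other psychological outcomes will similarly be analyzed using linear mixed models adjusted for randomization imbalance by covarying baseline levels of the outcome". Section 4.3 lists the self-report mediators among the tertiary outcomes.

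For the DMI, section 8.3 says "it is not necessary to adjust for baseline differences, as all participants exhibited opioid misuse at baseline".

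**The concern.** A change score fixes the coefficient on baseline at 1. With equal variances at the two visits, the best linear coefficient is the correlation between them, which the SAP puts well below 1. Subtracting the whole baseline then adds noise.

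Two consequences follow. First, the effect of treatment on a self-report mediator would be estimated one way as a tertiary outcome (baseline as covariate) and another, less precise way in the path model. The same applies to the BPI, between model (1) and its path model. The total effect being decomposed would then not be the effect that the trial reports. Second, Aims 2 and 3 ask whether treatment moves the mediator, and that randomised comparison would be less powerful than the data allow.

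**Working it through.** **Inputs.** Correlation between repeated measures: SAP section 6.2, "varying correlations between repeated measures, which ranged from .34 -.56 per outcome in the R03". This is given for outcomes; applying it to mediators is an assumption. Sample: 200 after attrition (section 6.2), 100 per arm. Two-sided alpha .05 (sections 4 and 6.2). Section 6.1 gives effect sizes of .50 to .84 for pain and opioid variables and none for mediators, so d = 0.4 is assumed.

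**The plan's own figures first.** The mediation text states no number. The nearest is Table 2, which uses the same kind of correlation. For the treatment-by-time interaction with 2 groups, 3 occasions, noncentrality N·3·f²/(1 − ρ), power .80 (assumed; the table states none) and N read as the total, the detectable f at ρ = .50 and N = 130 is 0.112, against the stated 0.11. All 12 cells match after rounding.

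**Variance on a randomised path.** Take outcome SD 1 at both visits and correlation ρ within arms.

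- Change score: V = 2(1 − ρ).
- Baseline as covariate: V = 1 − ρ².
- Ratio: 2(1 − ρ)/[(1 − ρ)(1 + ρ)] = 2/(1 + ρ).

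The standard error of the difference is √(2V/100), power is Φ(d/SE − 1.96), and the difference detectable with 80% power is (1.96 + 0.842)·SE.

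| | ρ = .34, change | ρ = .34, adjusted | ρ = .56, change | ρ = .56, adjusted |
|---|---|---|---|---|
| V | 1.320 | 0.884 | 0.880 | 0.686 |
| SE | 0.162 | 0.133 | 0.133 | 0.117 |
| Power at d = 0.4 | 69% | 85% | 85% | 93% |
| Power at d = 0.5 | 87% | 96% | 96.5% | 98.9% |
| Detectable difference (SD) | 0.455 | 0.373 | 0.372 | 0.328 |

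The variance ratio is 2/1.34 = 1.49 to 2/1.56 = 1.28, and the SE ratio 1.22 to 1.13. In sample-size terms, 200/1.49 ≈ 134 to 200/1.28 ≈ 156: 200 patients analysed by change carry the precision of 134 to 156 analysed with baseline as covariate.

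**Change or post value as response.** Once the baseline of the response is a covariate, this choice does not matter for the treatment coefficient. Subtracting baseline from the response lowers the baseline coefficient by 1 and leaves the treatment coefficient unchanged.

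**The mediator-to-outcome path.** This path is not randomised. Take a model in which each measure is a stable trait (variance ρ) plus a visit-specific state (variance 1 − ρ), with no true mediator effect.

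- *States correlated s at the baseline visit, traits uncorrelated.* The changes have covariance s(1 − ρ) and the mediator change has variance 2(1 − ρ), so the change-score slope is s/2: 0.10 at s = .2 and 0.15 at s = .3. Simulation with 100 per arm gave false rejection of about 5%, 11%, 30% and 56% at s = 0, .1, .2 and .3. With both baselines as covariates the rates were 5–6%, 5–6%, 6–9% and 6–13%.
- *Traits correlated t, no shared state.* Traits cancel in the differences, so the change-score slope is 0. With both baselines as covariates, write c = tρ; the slope is c(1 − ρ)/(1 + ρ − 2c²). At t = .4 and ρ = .34: c = .136 and .0898/1.303 = 0.069. At ρ = .56: c = .224 and .0986/1.460 = 0.068. Simulated false rejection at t = .4 was 5–6% with change scores and 14–17% with baseline adjustment; at t = .6, about 5% and 33–35%.

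**DMI.** Everyone is positive at baseline, so change equals follow-up status and no outcome noise is subtracted. Simulated false rejection on this path stayed at 4.5% to 5.6% even with shared baseline noise of .3.

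**The case against.** **Baseline covariates are unspecified, not excluded.** The mediation text does not say that the change scores are unadjusted, and it defers to sources not available here. That is fair. But the SAP names baseline covariates for its main treatment models, so a reader following section 8.4 as written would fit differences without them.

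**A reader might infer that change scores manufacture mediation and should be banned.** The documents do not support this. The inflated false rejection needs noise shared at the baseline visit. If the dependence lies in stable traits, the ranking reverses. The SAP gives neither correlation. For the DMI, the SAP's primary measure of the opioid misuse that its example names, the mechanism cannot operate. For attentional bias or psychophysiological mediators, nothing in the SAP suggests visit noise shared with a pain questionnaire.

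**A reader might also infer that every other continuous model in the SAP covaries baseline.** It does not: sensitivity variations d to f in section 8.3 use constrained longitudinal analysis, and the EMA growth model in section 8.4 has no baseline term. The contrast is with the main models for the BPI, opioid dose and psychological outcomes.

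**The precision loss may not reach the stated mediation test.** "We will test mediation by evaluating the significance of the joint product of the a and b paths", and as labelled the a path runs from treatment to outcome while treatment to mediator is c. Read literally, the product omits the treatment-to-mediator path. This labelling is a separate matter. It does mean that the loss is best stated path by path, and no effect on the product test has been shown here.

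**The work is exploratory.** It will be reported separately, and no primary or secondary treatment comparison depends on it. That limits the weight.

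**Conclusion.** The point holds as a loss of precision on the two paths that start from randomised treatment: treatment to mediator, and treatment to outcome for continuous outcomes such as the BPI. The variance is 1.49 to 1.28 times larger than need be and standard errors are 22% to 13% larger; at an assumed 0.4 SD with 100 per arm, power is about 69% to 85% instead of 85% to 93%. These figures assume that the outcome correlations of .34 to .56 apply to mediators and that variances are equal across visits. Randomisation keeps both estimates unbiased in either form. For DMI outcomes only the treatment-to-mediator loss applies. No claim of bias on the mediator-to-outcome path can be settled from the document. This is a modest improvement to an exploratory analysis.

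**What to change.** In the mediation paragraph of section 8.4, state that:

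1. The treatment-to-mediator equation includes the pre-treatment mediator as a covariate.
2. The treatment-to-outcome equation includes the pre-treatment outcome as a covariate for continuous outcomes. For the DMI no outcome baseline is needed.
3. For continuous outcomes, the mediator-to-outcome path is reported both with change scores and with post-treatment mediator and follow-up outcome adjusted for both baselines. Disagreement between the two is read as a sign that the path is sensitive to how baseline is handled.

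The cost is SAP wording and one extra fit per model for item 3. Table 1 already schedules the pre-treatment values, so no new data are needed. When editing, identify each path by the variables it connects as well as by its letter.
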